We will conduct a double-blind, placebo-controlled, two-period cross-over study (**Figure 1**). The order of treatment will be balanced (i.e., half start with KE and half start with Placebo). Participants (n = 60) will be familiarized with all the physical performance tests to minimize learning effects and undergo baseline assessments. Subjects will then be randomized to either the KE or Placebo condition. On the morning of Day 1, prior to administration of KE or Placebo, subjects will undergo Pre-Testing inclusive of a blood draw, physical, and cognitive performance. For that night, and the next 4 nights, all subjects will restrict their sleep by 50%. On the morning of Day 5, the same testing battery performed on Day 1 will be replicated. KE or Placebo ingestion will occur on Days 2, 3, and 4 (2 doses/day), and include 1 dose on Day 5. After a 2-wk washout period, during which time participants return to their normal sleep and exercise habits, they will replicate the exact same 5-day protocol except they will receive the opposite treatment.

[figure not shown]

Figure 1 | Experimental Design

Rationale for Design.

We expect to show that short-term sleep restriction combined with physical exertion is associated with disturbed glucose metabolism as well as impaired cognitive function and physical performance. Based on emerging animal and human evidence indicating that ketosis is associated with enhanced cognition and improved physiological tolerance and performance in response to physical exertion [25, 26], our central **hypothesis** is that KE ingestion will lessen the detrimental effects of sleep restriction on cognitive and physical performance. This will be the first work to specifically explore how ketosis impacts cognition in the context of sleep restriction and performance tasks.

Participants.

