This will be the first prospective study to compare responses between a group that receives a ketogenic diet and/or ketone supplements to a group that receives the same treatment undergoing a placebo. Statistical analyses will occur in collaboration with the OSU Center for Biostatistics. For data reduction purposes, z-scores within a given cognitive domain will be averaged to generate a composite measure for that domain. Prevs. post-stressor differences in the composite cognitive score will be calculated and summarized for all subjects across treatment arms and time points. Differences in cognitive scores between treatment arms will be analyzed using two-way repeated-measures ANOVA. An interaction term between time and treatment will test whether there was any carry-over effect. Normality and heteroscedasticity will be checked using residual plots. Sample size calculations were based on a randomized crossover design of male athletes, which found an effect size of 0.7 in pre- vs. post-test cognitive performance between placebo and KE [32]. Our sample size of 60 subjects has 96.5% power (α =0.05) to detect this effect size (standardized mean difference) between treatments.

REFERENCES

- 1. Shattuck, N.L., et al., *The role of sleep in human performance and well-being*. 2020, Oxford University Press.
- 2. 2019 Health of The Force. U.S. Army Public Health Center.
- 3. Fullagar, H.H., et al., Sleep and athletic performance: the effects of sleep loss on exercise performance, and physiological and cognitive responses to exercise. 2015. **45**(2): p. 161-186.
- 4. Belenky, G., et al., *Patterns of performance degradation and restoration during sleep restriction and subsequent recovery: A sleep dose-response study.* 2003. **12**(1): p. 1-12.
- 5. Smith, C.D., et al., *Sleep restriction and cognitive load affect performance on a simulated marksmanship task.* 2019. **28**(3): p. e12637.
- 6. Broussard, J.L., et al., *Impaired insulin signaling in human adipocytes after experimental sleep restriction: a randomized, crossover study.* 2012. **157**(8): p. 549-557.
- Hanlon, E.C. and E.J.P.o.t.N.A.o.S. Van Cauter, *Quantification of sleep behavior and of its impact on the cross-talk between the brain and peripheral metabolism.* 2011.
 108(Supplement 3): p. 15609-15616.
- 8. Spiegel, K., R. Leproult, and E.J.T.I. Van Cauter, *Impact of sleep debt on metabolic and endocrine function*. 1999. **354**(9188): p. 1435-1439.

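### Free improvement: compare Day 5 cognition adjusted for each period's Day 1 score, rather than leave the contrast to pre/post differences or an undefined ANOVA term

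*Protocol*

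**What the plan says.** The Protocol's Experimental Approach section sets the design: "We will conduct a double-blind, placebo-controlled, two-period cross-over study". Treatment order is balanced: "The order of treatment will be balanced (i.e., half start with KE and half start with Placebo". The same test battery is run on Day 1 and Day 5, and the five-day schedule is repeated in the second period, so each participant supplies four cognitive scores.

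The Data analysis section makes four statements that matter here:

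- On the outcome scale, it takes pre- versus "post-stressor differences in the composite cognitive score will be calculated and summarized for all subjects across treatment arms and time points".
- The inferential test follows as a separate step: "Differences in cognitive scores between treatment arms will be analyzed using two-way repeated-measures ANOVA".
- The interaction is given a different job: "An interaction term between time and treatment will test whether there was any carry-over effect".
- The planning effect is taken from a cited crossover in male athletes (an earlier study), "which found an effect size of 0.7 in pre- vs. post-test cognitive performance between placebo and KE". The power claimed for that effect is stated next: "Our sample size of 60 subjects has 96.5% power (α =0.05) to detect this effect size (standardized mean difference) between treatments".

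No statement uses the Day 1 score of each period as a covariate.

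On the order of events on Day 1, Experimental Approach says: "On the morning of Day 1, prior to administration of KE or Placebo, subjects will undergo Pre-Testing inclusive of a blood draw". The Supplementation section instead has product provided on the morning of Days 1 and 5 ahead of testing. Item 3 under Test Day 1 & 5 has the first dose taken before the cognitive battery starts.

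**The concern.** In a crossover each participant is already their own control. Pairing the two periods removes stable differences between people. Subtracting a Day 1 score in each period then removes only what is specific to that week, and it brings in the measurement error of two further scores. Regression on the Day 1 difference lets the data choose how much of it to remove, whereas a change score fixes that amount at all of it.

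Precision on the main cognitive question is at stake, not validity. The planning effect of 0.7 is large and comes from one study of male athletes, while this trial enrols men and women aged 18 to 40. If the true effect is smaller, the lost precision could decide the result, and the data needed to recover it are already being collected.

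**Working it through.** **1. The Protocol's own figure.** Inputs from Data analysis: n = 60, standardized difference 0.7, α = 0.05 (taken as two-sided; the sidedness is not stated). A paired t-test with zero correlation between the two treatment values has dz = 0.7/√2 = 0.495 and noncentrality 0.495 × √60 = 3.83. Power is 96.49% on 59 df and 96.48% on 58 df. The stated 96.5% reproduces.

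**2. The candidate contrasts.** Let D1 and D5 be a participant's KE-minus-placebo differences on Day 1 and Day 5. Assume that each has variance V, that their correlation is r, and that Day 1 is tested before any dose. If time in the ANOVA means Day 1 versus Day 5:

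- Time-by-treatment interaction: this is D5 − D1, the change contrast. Variance = V + V − 2rV = 2V(1−r).
- Treatment main effect: this is (D1 + D5)/2. It estimates half the Day 5 effect with variance V(1+r)/2. Doubled to the Day 5 scale, the variance is 2V(1+r).
- D5 adjusted for D1: variance = V(1−r²), apart from one degree of freedom.

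Ratios of adjusted variance to the alternatives:

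- Against change: V(1−r²) / [2V(1−r)] = (1+r)/2.
- Against the main effect: V(1−r²) / [2V(1+r)] = (1−r)/2.

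**3. Numbers.** The Protocol does not give r, so the values below are assumed. The equivalent n is 60 divided by the ratio against change. The power column takes 0.7 as being on the change scale and uses dz = 0.495/√ratio on 57 df.

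| r | ratio vs change | SE reduction | equivalent n for change scores | ratio vs main effect | power after adjustment |
|---|---|---|---|---|---|
| 0 | 0.50 | 29% | 120 | 0.50 | 99.96% |
| 0.25 | 0.63 | 21% | 96 | 0.38 | 99.7% |
| 0.5 | 0.75 | 13% | 80 | 0.25 | 99.2% |
| 0.8 | 0.90 | 5% | 67 | 0.10 | 97.8% |

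The case r = 0 arises when a participant's four scores are all equally correlated. Positive r means that scores from the same week resemble each other more than scores from different weeks.

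As an illustration with an assumed effect that is not in the Protocol: at 0.4 SD of change (dz = 0.4/√2), the change contrast has 58% power. The adjusted contrast has 86%, 78% and 70% at r = 0, 0.25 and 0.5.

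**4. Simulation.** Settings: n = 60, 30 per sequence, a period effect of 0.3 SD, within-period correlation 0.7 and cross-period correlation 0.7, 0.6 or 0.4. Since r = (within − cross)/(1 − cross), these give r = 0, 0.25 and 0.5. Over 4,000 runs each, the variance ratios were 0.51, 0.65 and 0.77. Both estimators were unbiased, and type I error was 4.5% to 5.5% for each.

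**5. Coding of sequence.** In the same simulation, with a 0/1 sequence indicator, the intercept is the effect in one sequence only and absorbs the period effect. Its type I error was 52%, 28% and 13%. With codes of +1/2 and −1/2 it was about 5%.

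**The case against.** **Change may not be the tested contrast.** A reader might infer that the plan tests Day 1-to-Day 5 change. The text does not say so: it has the differences calculated and summarized, and the test is an ANOVA of scores. The term equal to the change contrast is assigned to carry-over. This objection stands, and change as the tested contrast is only the likeliest reading. It does not rescue the plan, because the other available term, the treatment main effect, averages in Day 1 and also loses to adjustment.

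**The variance need not double.** A reader might infer that the plan doubles the variance. That is the r = 0 case only. At r = 0.8 adjustment saves 10%. At the planning effect, power is already high, so the gain there is small. The objection stands.

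**The power statement is not in error.** A reader might take 96.5% as proof that the plan intends change scores, or as a mistake. It is neither. The figure fits any paired contrast at 0.7/√2, so it is consistent with change without identifying it.

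**Change scores are valid, and covariates are often left to a SAP.** Change is unbiased, holds its size and suits the hypothesis that KE lessens a decline. That is why this is an efficiency point. The Protocol does, however, fix a model and an outcome scale, so the improvement belongs where those are stated.

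**Day 1 may not be a baseline.** Two sections place the dose before Day 1 testing and one places it after. This objection stands and conditions the recommendation. With a post-dose Day 1 score, both change and adjustment would remove part of any acute effect.

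**Conclusion.** This is a free improvement, not a validity fault. The plan describes and sizes the cognitive effect on the pre/post scale, leaves the treatment contrast in its ANOVA undefined, and does not use the period-specific Day 1 score as a covariate. Day 5 adjusted for Day 1 has between half (r = 0) and nine-tenths (r = 0.8) of the variance of the change contrast, and one-half to one-tenth of that of the treatment main effect over the same range.

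These sizes assume equal variance of the Day 1 and Day 5 differences, a pre-dose Day 1 score and no residual effect of the first period on the second Day 1. With unequal variances the ratio changes, but in large samples adjustment still does no worse, because a change score is the same regression with its slope forced to 1.

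**What to change.** First reconcile Experimental Approach, Supplementation and Test Day 1 & 5 on whether Day 1 cognitive testing comes before or after the first dose. The Day 1 score is a valid covariate only if it is pre-dose.

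If it is, put two sentences in Data analysis:

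- Name the Day 5 KE-minus-placebo difference in the composite as the treatment contrast.
- Estimate it by regressing each participant's Day 5 difference on their Day 1 difference (uncentred) and a sequence code of +1/2 and −1/2, with the intercept as the KE effect.

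An equivalent mixed model has treatment, period and the within-participant part of the Day 1 score. The raw Day 1 score with a random participant effect is not equivalent. A 0/1 sequence code must not be combined with reading the intercept as the effect.

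Keep change scores as descriptive summaries. The cost is the two sentences and one degree of freedom; no new data are needed.

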It is understood by all concerned that an excessive rate of withdrawals can render the study uninterpretable, therefore, unnecessary withdrawal of participants should be avoided. Should a participant decide to withdraw, all efforts will be made to complete and report observations as thoroughly as possible and documented in the eCRF.

Serious Adverse Event Reporting Instructions.

If in the opinion of the Investigator the event meets the criteria of a SAE the following procedures will be followed:

- The Investigator will notify Institutional Review Board (IRB) of the SAE within the parameters and timeframe specified under the IRB Standard Operating Procedures (SOP). An initial report followed promptly by a complete report will be forwarded to the IRB, when applicable.
- If a participant is hospitalized or hospitalization is prolonged due to the SAE, the hospital discharge summary will be obtained if possible.
- If a death occurs and an autopsy is performed, a copy of the autopsy report will be obtained if possible.
- All efforts must be undertaken to obtain follow-up information promptly.

Recording of Adverse Events.

All AEs (AE or SAE) will be recorded on the AE study documents. For participants who have an ongoing AE at their final study visit, follow-up information will be captured in the AE eCRF page which will be completed after 30 days.

Serious Adverse Event Follow-Up.

For all ongoing SAEs occurring during the study, the Investigator must submit follow-up reports regarding the participant's subsequent course. All SAEs that are ongoing at the end of the study or upon discontinuation of the participant's participation must be followed until either:

- The event resolves, or
- The event/condition has stabilized (e.g., in the case of persistent impairment), or
- The event returns to baseline, if a baseline value is available, or
- The participant dies, or
- The event can be attributed to other than the study beverage, or to other than the study conduct.

Participant Compensation.

Participants who complete all study duties will be compensated with a \$300 PCard or a check. No compensation will be provided for completing the screening visit. Payments will be prorated by condition: each 5-day condition will result in \$150; completion of both conditions (KE and Placebo) will result in \$300. Any external costs associated with the study (i.e., transportation) will be covered by the study team.

Data analysis.

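### The cognitive analysis of this two-period crossover names only 'time' and 'treatment': period and sequence are not named, 'time' is undefined, and the interaction labelled as a carry-over test is, on the reading that can be fitted, the treatment effect itself.

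*Protocol*

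**What the plan says.** Under Experimental Approach the protocol describes a "double-blind, placebo-controlled, two-period cross-over study" in which "half start with KE and half start with Placebo". The second period follows a two-week washout and repeats the same five-day schedule.

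The Data analysis section averages z-scores within each cognitive domain into a composite and calculates pre- versus post-stressor differences in it. It then commits to a model: "Differences in cognitive scores between treatment arms will be analyzed using two-way repeated-measures ANOVA". The next sentence says that an interaction between time and treatment will test for carry-over. Time is not defined as pre/post or as period. Neither period nor sequence is named as a factor anywhere in the protocol.

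The planning effect is a pre/post one: the cited study "found an effect size of 0.7 in pre- vs. post-test cognitive performance between placebo and KE". The stated result is "Our sample size of 60 subjects has 96.5% power" at a 5% level.

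**The concern.** In a two-period crossover the participant is randomised to an order, so the treatment contrast is made within person across periods. A model that leaves out period treats any systematic difference between the first and second period as unexplained variation in the KE-minus-placebo differences. Balanced order keeps that difference from biasing the estimate only while both orders finish in equal numbers. It does not take it out of the error term.

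A period effect is plausible here. The protocol itself provides familiarization to limit learning. Table 1 has the cognitive tests at familiarization, Day 1 and Day 5, and the second period repeats Days 1 and 5, so a participant meets the battery up to five times.

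The interaction matters separately. If it is the treatment effect on change, then a positive treatment result would, by the protocol's wording, be reported as evidence of carry-over.

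**Working it through.** **1. What can 'time' mean?**

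- *Time is period.* There are four treatment-by-period cells, and each participant occupies two of them (KE in period 1 and placebo in period 2, or the reverse). A repeated-measures ANOVA with both factors within person needs all four cells per person, so it cannot be fitted.
- *Time is pre/post.* Each participant has all four cells (KE pre, KE post, placebo pre, placebo post), so the ANOVA can be fitted, and it matches the pre/post planning effect. The interaction is (KE post − KE pre) − (placebo post − placebo pre), which is the treatment effect on change. It carries no information on carry-over, and there is no period term.

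The rest of the working takes the second reading, where the interaction test is a paired t test on D, the KE-minus-placebo difference in change.

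**2. Which period effects matter?** A practice gain shared by Day 1 and Day 5 of the same period cancels in the change. A flattening learning curve does not. The change in period 1 contains the gain from exposure 2 to 3, and the change in period 2 the gain from exposure 4 to 5. Let p be the period 2 minus period 1 shift in the change. The documents give no value, so 0.5 and 1.0 are assumed.

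**3. The plan's own figure.** Inputs from Data analysis are n = 60, effect 0.7 and α = 0.05 (two-sided assumed). With an SD of 1 for one period's change and zero within-person correlation (assumed), Var(D) = 2 and the standardised difference is 0.7/√2 = 0.495. Noncentral t power on 59 degrees of freedom is 96.49%, which reproduces 96.5%. With period in the model (58 degrees of freedom) it is 96.48%.

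**4. Period left out, 30/30 completers.** D has mean δ − p in those who start with KE and δ + p in those who start with placebo. The overall mean is δ, so there is no bias, and its true variance is still 2/60. The variance estimated without period is close to 2 + p², so the standard error is too large by √((2 + p²)/2):

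- p = 0.5: √1.125 = 1.061, or 6%
- p = 1.0: √1.5 = 1.225, or 22%

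Simulation (200,000 trials per setting):

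| Assumed p | Type I error, no period | Power, no period | Power, period modelled |
|---|---|---|---|
| 0 | 5.0% | 96.5% | 96.5% |
| 0.5 | about 3.7% | about 95.3% | about 96.5% |
| 1.0 | about 1.7% | about 91.2% | about 96.5% |

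With period modelled, type I error is about 5% throughout. Putting the inflated SD straight into the noncentral t formula would give 94.5% and 86.8%. That overstates the loss, because a fixed shift adds nothing to the sampling variance of a balanced mean.

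The inflation depends on the assumed correlation. At 0.5, Var(D) = 1 and the factor is √(1 + p²), which is 12% at p = 0.5 and 41% at p = 1.0. Power at the planned effect with no period shift would then be 99.96%.

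**5. Unequal completion.** Without period, bias = p × (n placebo-first − n KE-first)/n. For an assumed 30 KE-first and 24 placebo-first completers this is −6/54 × p = −0.11p. That is −0.06 at p = 0.5 and −0.11 at p = 1.0, in within-subject SD, against a planned 0.7. With the shift working against KE in this way, power is about 88.6% and 72.7%, compared with about 94.4% when period is modelled. The direction reverses if p changes sign or the other order loses more participants.

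**The case against.** The strongest objection is that time may mean period. The carry-over sentence is coherent only on that reading, since treatment-by-period is the usual sequence or carry-over contrast. The pre/post differences are also calculated first, so the remaining time points could be the two periods. A reader might therefore infer too much from a flat claim that the model has no period term. This stands in part: the absence is the likeliest reading, not a stated fact. It does not rescue the plan, because the named method cannot be fitted fully within person with period as a factor. Either the method or the carry-over sentence has to change.

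A reader might also infer that one-period participants will be discarded, since classical repeated-measures ANOVA uses complete cases and, on compensation, "Payments will be prorated by condition". The documents do not support that as a finding. No such rule is stated, the payment provision is administrative, and missing-data handling may sit in an SAP that is not shown.

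Finally, the harm is conditional. The outcome is a change score, familiarization covers the cognitive tests, and no document gives a period effect. With equal completion the error is on the conservative side, and at a shift of 0.5 the power loss is about one percentage point. All of that stands and limits the size of the point. A shift of a full within-subject SD is an illustration, not an expectation.

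**Conclusion.** The point holds as a mismatch between design and stated model. Period and sequence are not named, time is undefined, and on the reading that can be fitted the interaction is mislabelled as a carry-over test. That much needs no assumption about data.

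The numerical cost rests on three assumptions: a non-zero period effect on the pre/post change (0.5 or 1.0 used here), zero within-person correlation (the value that reproduces the stated power), and, for bias, unequal completion by order (30/24 used here). With equal completion the cost is modest and conservative. With unequal completion it becomes bias and a larger loss of power. The plan should be changed, but this would not by itself invalidate the trial. It would go too far to read it as saying that the analysis certainly omits period, that it is biased as designed, or that participants with one period are certain to be dropped.

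**What to change.** Define time in the Data analysis section. Replace the two-way ANOVA by a linear mixed model on each period's pre/post change in the composite score, with treatment, period and sequence as fixed effects and participant as a random effect, using all available periods. Delete the statement that the time-by-treatment interaction tests carry-over.

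One matter comes first. Experimental Approach places Day 1 testing before KE or placebo is given, while item 3 under Test Day 1 & 5 places the first dose before the cognitive battery. These passages must be reconciled before the Day 1 score is used as a pre-treatment baseline, either within the change score or as a covariate. If Day 1 testing follows a dose, subtracting or adjusting for it could remove part of the treatment effect.

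The cost is one or two degrees of freedom and a rewording. No new data are needed, and power at the planned effect is unchanged to the first decimal (96.49% against 96.48%).

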Participants will be recruited through posted flyers, e-mails, word of mouth, and by using ResearchMatch through the OSU CCTS. Print and email advertisements will instruct interested individuals to call the study center ([name] Lab, Kinesiology Program) for additional information about the study. Participants may either respond to the email address to set up a phone call or may call during the phone-in hours. One of the key personnel involved in the project will describe the study and determine preliminary qualifications by conducting a scripted phone interview. Participant answers to qualifying criteria questions will be recorded to assess whether or not the person calling meets the initial qualifying criteria. If it is determined that the interested participant does meet the initial qualifying criteria, an appointment will be made for the interested participant to visit the study center for a screening meeting.

Supplementation.

The ketone ester (KE) supplement we plan to use the C6 Diester (Metabolic Switch), which delivers rapid (<30-min) and sustained (~5-hr) ketosis in a predictable and dosedependent manner. We have used this particular KE in previous studies at OSU (e.g., protocol number 2020H0005 and 2021HO425) and it is well tolerated and consistently elevates ketones into the desired range. Metabolic Switch and Placebo will be provided in a flavor and volume matched single serving nondescript plastic container in the morning prior to testing on Days 1 and 5, and then again in the evening during the sleep restriction period. The product will be consumed twice per day: once in the morning and once in the evening. Product will be distributed in a blinded manner by people not involved with testing. For more details regarding the supplement refer to *Supplementation* section below.

C6 Diester and finished product (Metabolic Switch) is manufactured under good manufacturing practice conditions for BHB Therapeutics Ltd (and its parent company, Juvenescence Ltd). BHB Therapeutics conducted a program of safety and efficacy testing

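### The carry-over sentence leaves 'time' undefined; if time means Day 1 versus Day 5, the term it calls carry-over is the KE efficacy contrast

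*Protocol*

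**What the plan says.** The Data analysis section of the protocol sets out three steps. First, pre- versus "post-stressor differences in the composite cognitive score will be calculated and summarized for all subjects across treatment arms and time points". Second, "Differences in cognitive scores between treatment arms will be analyzed using two-way repeated-measures ANOVA". Third, "An interaction term between time and treatment will test whether there was any carry-over effect". The two factors of the ANOVA are not named, time is not defined, and no term is identified as the test of the KE effect.

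The sample size in the same section rests on an earlier cross-over study "which found an effect size of 0.7 in pre- vs. post-test cognitive performance between placebo and KE". With 60 subjects and alpha 0.05 the stated power is 96.5%.

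The Experimental Approach section gives the layout. Half the subjects start on KE and half on placebo. Within each period, "On the morning of Day 5, the same testing battery performed on Day 1 will be replicated". After the washout "they will replicate the exact same 5-day protocol except they will receive the opposite treatment". The hypothesis, under Rationale for Design, is that KE reduces the harm that sleep restriction does to cognitive and physical performance.

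**The concern.** A protocol may leave model details to a statistical analysis plan. This sentence does more than leave a gap: it fixes what the time-by-treatment interaction means. In a cross-over trial with a pre and a post test in each period, that phrase can denote two different contrasts, and only one of them concerns carry-over.

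If the analyst takes time as test day, the term called carry-over is the treatment effect on the decline from Day 1 to Day 5. A trial that succeeds would then report its main result as carry-over, and a trial with no KE effect would report the same term as reassurance that there was none.

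**Working it through.** **Inputs.** From the protocol: 60 subjects, two sequences of equal size (60/2 = 30 each), tests on Day 1 and Day 5 of each period, standardized difference 0.7, alpha 0.05, power 96.5%. Assumed, because the protocol does not give them: two-sided test, change-score SD 1, and correlation r between a subject's two change scores of 0, 0.2 or 0.5.

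**1. The plan's own figure.** For a paired comparison of change scores the SD of the KE-minus-placebo difference is √(2(1 − r)). With r = 0 it is √2 = 1.414, and the noncentrality is 0.7 × √60 / 1.414 = 3.83. Noncentral-t power is 96.5% (58 or 59 df). The stated figure is reproduced.

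**2. Time = test day.** Each subject fills all four treatment-by-day cells, so the named ANOVA can be run. Its interaction is

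(Day 5 − Day 1 on KE) − (Day 5 − Day 1 on placebo).

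This is the paired contrast of step 1. On simulated data the interaction F was 7.7675, equal to the squared paired t on the change difference (7.7675, p = 0.0071 for both). With no carry-over at all, the proportion of trials in which the term is significant is therefore the power for the KE effect:

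| True KE effect | r = 0 | r = 0.2 | r = 0.5 |
|---|---|---|---|
| 0.2 | 19% | 23% | 33% |
| 0.3 | 37% | 44% | 63% |
| 0.5 | 77% | 85% | 97% |
| 0.7 | 96.5% | 98.8% | >99.9% |

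**3. The condition on step 2.** The term is the full efficacy contrast only if Day 1 is tested before the first dose. Experimental Approach puts Day 1 testing before dosing; Supplementation and the Test Day 1 & 5 procedures put the dose first. As an illustration, if Day 1 were post-dose and KE gave 0.7 on both days, the contrast would be 0.7 − 0.7 = 0.

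**4. Time = period, outcome = change score.** Each subject has two of the four treatment-by-period cells. Write KE1 for the mean change on KE in period 1, and so on. The interaction is

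(KE1 − PL1) − (KE2 − PL2) = (KE1 + PL2) − (PL1 + KE2).

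This is the difference between the sequences in the sum of the two changes, a recognised carry-over contrast. With a true KE effect of 0.7 and no carry-over, it rejected in 5.0% of simulated trials, its nominal rate. A routine that needs a complete within-subject crossing stops with a collinearity error on this layout. A mixed model with a random subject effect fits it and gives the same test as the sequence term.

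**5. Precision of the sequence contrast.** SE = √(2(1 + r)) × √(2/30); the 95% half-width uses t(58) = 2.002.

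- r = 0: 0.365 × 2.002 = 0.73
- r = 0.2: 0.400 × 2.002 = 0.80
- r = 0.5: 0.447 × 2.002 = 0.90

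At r = 0 its power against a carry-over of 0.7 in the change score is 47%.

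**The case against.** The strongest reply is that the text favours period. A Day 1 to Day 5 difference already uses both days, so it cannot be summarised over them; the time points left in that sentence are the two periods. Treatment by period on change scores is the usual carry-over test, which is what the next sentence says the interaction does. This stands as a real alternative reading. It does not settle the matter, because the ANOVA sentence speaks of cognitive scores, not differences, and the ANOVA it names fits treatment by day.

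A reader might go further and infer that the period reading fails too, since a repeated-measures ANOVA cannot estimate that interaction. The protocol does not support this. A mixed model estimates it, and what remains is a quibble over the name of the method.

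A third reply is that the definition of time belongs in the analysis plan. That holds for the choice of covariance or random effects. It does not excuse a sentence that assigns a meaning to the term, since on one natural reading that meaning is wrong.

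Finally, carry-over that is equal on both period-2 test days cancels from the change score. Neither contrast can show it, but it does not bias a change-based KE estimate either, so it is not a ground for complaint.

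**Conclusion.** The sentence should be corrected, with moderate confidence. If time is test day, it labels the hypothesis test as carry-over: at the planning effect of 0.7 with no carry-over, the term is significant in about 96.5% of trials, given change-score SD 1, between-period correlation 0 and 60 subjects. It is the full efficacy contrast only if Day 1 testing is pre-dose. If time is period, the sentence is loosely worded and not wrong. The protocol does not show which is meant.

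Three stronger conclusions might be inferred, and none is supported. The protocol does not show that efficacy will in fact be reported as carry-over. The sample size is not at fault: 96.5% reproduces, and no decision rule hangs on the term. Nor is there reason to expect sizeable carry-over: the protocol describes the product as one that "delivers rapid (<30-min) and sustained (~5-hr) ketosis", and the second period starts "After a 2-wk washout period, during which time participants return to their normal sleep and exercise habits". The point is the label on the term.

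**What to change.** Replace the carry-over sentence in the Data analysis section with wording such as:

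> The KE effect is the treatment term in a mixed model for the Day 1 to Day 5 change in composite score, with treatment, period and sequence as fixed effects and subject as a random effect. The day-by-treatment interaction is not a carry-over test. Carry-over is described by the sequence term (the sum of the two change scores) with a 95% confidence interval and does not determine the treatment analysis.

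The sequence term stays descriptive because its half-width at 30 per sequence is about 0.73 to 0.90, as large as the planning effect itself or larger.

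One step comes first. Experimental Approach, Supplementation and the Test Day 1 & 5 procedures must be reconciled on whether Day 1 testing precedes the first dose. Both the change score as efficacy outcome and any comparison of Day 1 scores between periods as a further look at carry-over depend on the answer. This review takes no position on which statement is right.

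The cost is one sentence replaced by a short paragraph, plus that reconciliation. No extra data or participants are needed, and the sample size stands.
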